#### **4.2 Procedures for Minimizing Risks**

Investigators involved with this study have a great deal of expertise with the management of tetraplegic patients and with craniotomies. The surgical team has over 16 years of experience with deep brain stimulation implants with over 1600 DBS implants for various indications. The study inclusion/exclusion criteria have been developed to select those who would most likely benefit from this study as well as excluding those with higher risks. Study participants will be monitored after surgical implantation in neurosurgical and physiological monitoring units with personnel experienced in the care of complex neurosurgical participants and monitoring neurological status. In the case of cerebrospinal (CSF) leakage or pain, patients will be managed per the standard clinical practice. In case of infection that is not responsive to antibiotic treatment or allergic reaction to the implanted device, the device will be explanted.

Upon completion of the study, participants will have the entire cortical implant system surgically removed. The procedure for removing the device is similar to those of the implant procedure.

Risks for removal are similar to insertion: infection, bleeding, need for further surgery, and seizures.

Post-surgical removal the participants will be asked to come for post-surgery follow up appointments to remove stitches/sutures and wound caring.

Risks are minimized in all of the non-surgical procedures including blood drawing and the neuroimaging procedures by having trained and highly experienced personnel performing all those tasks.

Participants may also terminate from the study if they wish at any time. Study participants may also wish to discontinue participation for any reason. Cortical implant systems will also be removed if the participant/representative asks for removal. Participants who prematurely withdraw from the study due to an adverse event will be followed (e.g. telephone contact, and/or follow-up visits, etc.) until resolution of the event. In addition, a designated investigator will have access to treatment status at all times and provide that information to appropriate medical personnel in the event of medical emergencies. Risks to confidentiality are negligible in this protocol, since participants will not be identified by name, or by any personal data, in any summary reports or publications. CRFs will be maintained in locked files and password-protected databases behind the Ohio State University Wexner Medical Center firewall. Data and safety monitoring activities for this study will continue until all participants have completed their participation in the study.

#### **4.3 Potential Benefits**

The intended purpose of neuroprosthetics is to develop devices to replace or improve the function of an impaired nervous system. Thus far, BCI systems have been successful in controlling power chairs, robotic devices and more recently, upper limb movement in animals. Functional electrical stimulation (FES) systems have been created that stimulate muscles and restores functional movement in paralyzed limbs. This is the first study in humans to combine both systems, a BCI and functional electrical stimulation, to produce real-time control of a paralyzed limb.

#### **4.4 Study Justification**

The target population will be people with C4-6 ASIA A spinal cord injuries (motor and sensory complete neurologic injuries ) who are more than 1 year post injury and who are neurologically stable. This population has no potential for additional neurological recovery of functional movement. People with this level of paralysis are totally dependent in all aspects of self-care. Restoration of functional movement in this population requires exploration of neuroprosthetic applications to increase functional movement that has quality of life implications. This BCI system is the first attempt to utilize cortical sensors and a high resolution stimulation system to bypass the injured spinal cord and produce volitional movement in humans.

The sleeve configuration of the NMES represents an incremental step toward portability for the system. The sleeve provides a less operator-dependent, more convenient application and removal of the electrode cuff. The electrodes and circuitry are otherwise identical to the cuff.

This reanimation study offers a unique opportunity to study the neural mechanisms of motor awareness, such as sense of agency or movement intentions. Agency is the sense that we control the actions of our own body (Gallagher, 2000; Jeannerod, 2003) and is a fundamental aspect of the experience of self. In this study, normal efferent and afferent sensorimotor information is replaced by the reanimation system and visual feedback, respectively. Congruent and incongruent visual feedback presented via virtual reality may provide important information about the fundamental mechanisms of self-awareness. This is clinically relevant to developing neuroprosthetics that maximize user acceptance by enhancing integration with the users' body image. In addition, we will study whether using virtual reality (VR) can provide a more efficient way to train motor cortex neural decoders.

#### **4.5 Device Description**

The Neural Bridging System (as shown in Figure 2) is comprised of a Blackrock Microsystems Neuroport device, a personal computer (PC) which runs the re-coding algorithm, and a non-invasive Neuromuscular Stimulator. The Neuromuscular Stimulator has been reviewed and

approved by a registered IRB for use in a study with human participants. In this study both wrist and individual finger movements have been demonstrated (Bouton and Annetta 2012).

The Neuromuscular Stimulator, designed by Battelle Medical Products, is a non-significant risk investigational device; however it is included in this submission for completeness (since the two devices will be used together in the study). In addition, note the Neural Bridging System will be used in support of an IDE study to demonstrate proof-of-concept in a clinical environment. As such, the results from this IDE study will be used to determine feasibility of the product concept and will not be used to support a regulatory clearance or approval submission.

#### **4.5.1 Clinical Safety**

Safety risk management for the Battelle BCI-NMES (updated and inclusive of VR device) was performed in accordance with Battelle Process and Product Development SOP 65, Safety Risk Management Procedure, which complies with the requirements of ISO 14971:2007, *Medical devices – Application of risk management to medical devices*. A safety risk management plan was put in place, and potential hazards associated with the use of the device were identified. The risks of the identified hazards were evaluated against the risk acceptability criteria documented in the plan, and controls identified for risks that exceeded the acceptability thresholds. The identified risk controls were incorporated into the product design or clinical trial protocol, as appropriate. A summary of the analysis is included below.

##### Hazard Analysis Summary (Without VR Device)

A hazard analysis was conducted in accordance with D8208-020 (a document within Battelle Medical Devices Quality System), Neurobridge Clinical Trial Safety Risk Management Plan, and identified the following potential hazards associated with the use of the device:

- Electromagnetic energy
- Thermal energy
- Biological
- Chemical
- Biocompatibility
- Functional
- Use error

[figure not shown]
- Installation/Service/Calibration
- Warnings

Analysis of potential hazard causes and evaluation of the risk of potential harm was conducted in accordance with D8208-020. The potential hazards required risk controls and the implemented risk control measures are detailed in the following table.

[figure not shown]
Potential Hazard	Potential Harm	Risk Control Measures
Electromagnetic energy	Participant/Operator electrical shock; burns	1. Design in accordance with Clause 8.5.1 of IEC 60601-1:2005 2. Current limiting safety circuit (on every channel) 3. Fuse on high voltage power 4. Clinical trial protocol excludes participants requiring use of life supporting/sustaining equipment 5. Clinical trial protocol excludes participants requiring use of critical health monitoring equipment 6. Electrostatic discharge warning label applied to device in area of NSC connectors
	Participant injury or unnecessary medical intervention	1. Clinical trial protocol excludes participants requiring use of life supporting/sustaining equipment
Biological	Participant contact dermatitis or infection	1. NSC materials and conduction enhancer in contact with the Participant are compliant with ISO 10993-1 requirements for limited exposure skin contact. 2. Clinical procedure specifies to not reuse the conduction enhancer.
Chemical	Participant/operator allergic reaction or infection	1. The conduction enhancer in contact with the Participant are compliant with ISO 10993-1 requirements for limited exposure skin contact

		
2. The NSC materials in contact with the Participant are compliant with ISO 10993-1 requirements for limited exposure skin contact
 
3. Participant monitored for allergic reaction to conduction enhancer that could result in classification as clinical adverse event

Biocompatibility	Participant/operator allergic reaction or infection	
1. The conduction enhancer in contact with the Participant are compliant with ISO 10993-1 requirements for limited exposure skin contact
 
2. The NSC electrode material in contact with the Participant are compliant with ISO 10993-1 requirements for limited exposure skin contact
 
3. Conduction enhancer formulation stable when subjected to anticipated storage conditions
 
4. Conduction enhancer formulation stable when subjected to electrical current

Function (inappropriate output)	Participant electrical shock; burns	
1. Current limiting safety circuit
 
2. Fuse on high voltage power supply
 
3. Incoming parts inspection to verify electrode size

User error (improper operation)	Participant electrical shock; burns	
1. Current limiting safety circuit (on every channel)
 
2. Fuse on high voltage power supply

Installation, service or maintenance	Participant electrical shock or burns	
1. Operator trained on clinical procedure to ensure application of conduction enhancer

The risks of harm for all other identified potential hazards were deemed broadly acceptable under the risk acceptability criteria established in D8208-020. Details of the potential hazards identified and evaluation of the risk of potential harm are provided in D8208-022, Neurobridge Clinical Trial Hazard Analysis.

[figure not shown]
**Figure 2. Overall System Diagram with Additional Details.**

**Figure 3. Neuromuscular Stimulator in Able-Bodied Study**

Hazard Analysis Summary (With VR Device):

An analysis was conducted by Battelle concerning the use of the VR device with the Battelle BCI-NMES(D8208-051). The risks of adding the Oculus Rift virtual reality headset to the NBS may increase the risk of electrical shock, however, due to the design of the NBS, the risk is not perceived to be significantly increased over wearing the headset without the NBS.

**Figure 4. Block diagram of the virtual reality headset used with the Neural Bridging System**

Risks Associated with the Oculus Rift Virtual Reality Device Alone:

- Seizures (1 in 4000 people)
- Electrical shock
- Repetitive stress injury such as muscle, joint, or skin pain
- Eye discomfort, eye muscle twitching, visual problems
- Dizziness
- Skin irritation

Risks associated with VR use will be mitigated by close patient monitoring, exclusion of patients with history of seizure or pacemaker, electrical isolation from the Neural Bridging System, and periodic device monitoring by the OSU Clinical Engineering Department. The VR device has

passed Clinical Engineering inspection to verify that no significant current is leaking from the electrical components of the device.

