##### **Exclusion Criteria:**

- No active wound healing or skin breakdown issues.
- No history of poorly controlled autonomic dysreflexia.
- Medical contraindications for general anesthesia, craniotomy, or surgery.
- Diagnosis of acute myocardial infarction or cardiac arrest within previous 6 months.

- Participants with any type of destruction and/or damage to the motor cortex region as determined by MRI.
- Dementia
- Psychiatric disturbances
- Other implantable devices such as heart/brain pacemakers
- Participants who rely on ventilators
- Co-morbid conditions that would interfere with study activities or response to treatment, which may include:
  - Life expectancy < 3 years
  - Severe chronic pulmonary disease
  - Confirmed seizure disorder that requires continued clinical care
  - Local, systemic acute or chronic infectious illness
  - Life threatening cardiac arrhythmias
  - Severe collagen vascular disorder
- Kidney failure or other major organ system failures History of a neurological ablation procedure.
- Labeled contraindication for MRI.
- History of hemorrhagic stroke.
- History of HIV infection or ongoing chronic infection (such as tuberculosis).
- Pregnant or of child-bearing potential and are not taking acceptable methods of contraception.

Participation in another investigational device or medication trial

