### **3.2.4 Phase IV - Follow-up**

The subject will have the device explanted when the study team and Principal Investigator have determined the subject is healthy enough to undergo explantation. After explantation surgery, participants will be asked to complete the same fMRI, neurophysiological recordings, neuropsychological tests, and TMS procedures as they did during the baseline phase.

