### **Transcranial magnetic stimulation (TMS)**

To complement the fMRI motor mapping of the motor cortex that is being used for pre-surgical implant location planning and post-explant evaluation of motor cortex plasticity, we will also include transcranial magnetic stimulation (TMS) pre-implant and post-explant to map the hand and arm area of the motor cortex. TMS is a non-invasive brain stimulation method that delivers a magnetic pulse through the surface of the skull to the motor cortex. This induces a depolarization of neurons in the corticospinal tract, which results in a twitch of peripheral limb muscles innervated by that brain region. This modality is commonly used clinically as an alternative to fMRI for pre-surgical motor mapping to assist in planning prior to brain surgery. It is used experimentally to investigate corticospinal tract plasticity associated with motor recovery, e.g., after stroke. Potential risks include seizures (2%, mostly among patients who were previously known to have seizures) and headache. Mapping of the hand/arm area with MRI-navigated TMS in patients with spinal cord injury serves 3 purposes: 1) it validates the cortical motor maps obtained through fMRI; 2) it distinguishes the sectors of cortical motor maps that are capable of controlling voluntary motion through the corticospinal tract in the spinal cord from areas that have been rendered mute from cord injury; and 3) it allows for quantification of plasticity, or change in sectors of motor maps that are capable of controlling voluntary motion through the corticospinal tract after stimulator explant.

We will perform TMS pre-implant (baseline, phase I) and post-explant (follow-up, phase IV).

We will deliver navigated TMS based on the patient's brain MRI scans to stereotactically identify and target near the "hand knob" of the primary motor cortex on the central sulcus.

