#### **4.1.4 Documentation of Adverse Events**

All AEs from the time the study informed consent is signed through the time of device explantation will be recorded as AEs on the study adverse event log; each event being documented separately. Any adverse event occurring after this time and is considered related to the device or therapy by the Principal Investigator will be reported. AEs and SAEs will be followed until:

- AE is resolved and has returned to normal/baseline or has stabilized
- Subject has withdrawn from the study
- AE is judged by the investigator to be no longer clinically significant
- Study closure at which time, the responsibility for following any ongoing AEs will be transferred to the incoming clinical care team.

The Principal Investigator will serve as point of contact to which the team will report adverse events. All non-serious adverse events will be reported to the FDA and to The Ohio State University Institutional Review Board (IRB) during the annual reporting period.

Relatedness will be determined for all events according to the following criteria:

- **Definitely related:** The event is resolved by discontinuing stimulation and another cause cannot be identified.
- **Probably related:** The event resolves upon discontinuing stimulation and cannot be reasonably explained by the subject's current clinical state or any other cause.

- **Possibly related:** The event was likely caused by the subject's current clinical state, , however, the effect of stimulation cannot be ruled out.
- **Unlikely related:** The event did not occur temporally to stimulation and can be explained by the subject's current clinical state or any other cause.
- **Unrelated:** The event is explained by the subject's current clinical state or any other cause.

For purposes of determination of a UADE the following categories will be considered related: “definitely related” and “probably related”.

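### All-event adverse event logging ends at explantation although other sections run it to study exit, and the seizure exclusion credited as a VR control is not in the eligibility criteria

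*Combined protocol and SAP*

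**What the plan says.** **Adverse event window.** Section 4.1.4 sets the logging rule: "All AEs from the time the study informed consent is signed through the time of device explantation will be recorded as AEs". For the time afterwards it says: "Any adverse event occurring after this time and is considered related to the device or therapy by the Principal Investigator will be reported". Section 4.1.5 sends serious events to the safety committee, the IRB continuing review and the FDA annual report, but only those reported within the period that 4.1.4 defines.

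Section 4.1 gives a different window. It makes the investigators responsible for evaluating, monitoring and documenting events, and has participants evaluated from consent until the study closes or they leave it. Section 4.1.1 makes the safety endpoint a characterisation of every adverse event in every participant, with a comparison between study phases.

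**What happens after explantation.** Section 3.2.4 says that "participants will be asked to complete the same fMRI, neurophysiological recordings, neuropsychological tests, and TMS procedures as they did during the baseline phase". Section 4.2 adds: "Risks for removal are similar to insertion: infection, bleeding, need for further surgery, and seizures". Section 3.2.5 says of TMS: "Potential risks include seizures (2%, mostly among patients who were previously known to have seizures) and headache".

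**Seizure history.** The VR part of the hazard analysis in 4.5.1 says: "Risks associated with VR use will be mitigated by close patient monitoring, exclusion of patients with history of seizure or pacemaker". The opening of 4.5.1 says: "The identified risk controls were incorporated into the product design or clinical trial protocol, as appropriate". The matching item in the exclusion criteria of 3.1.1 is "Confirmed seizure disorder that requires continued clinical care", given as one example of co-morbid conditions that would interfere with the study.

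**The concern.** The two adverse event windows cannot both be followed. If staff work from 4.1.4, which is the section headed as the documentation rule, an event after explantation enters the record only when the principal investigator links it to the device or therapy. A serious event not so linked would also miss the 4.1.5 route to the safety committee. The period affected contains recovery from the removal operation, the repeat TMS, and the post-explant neuropsychological tests, which 3.2.5 itself treats as a safety question.

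The phase comparison in 4.1.1 would then set partial capture after explantation against full capture before it. With at most 5 participants the comparison can only be descriptive, but a description that counts events differently by phase can mislead, and each lost event matters.

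The seizure issue is separate. A control that the hazard analysis relies on is broader than the criterion that would put it into effect at screening.

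**Working it through.** The plan states no figure on this point, so there is none to reproduce. The check is a comparison of texts followed by a short calculation of the time affected.

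**1. The windows side by side**

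| Section | Which events | Until when |
|---|---|---|
| 4.1 | any possible event, evaluated and documented | study closure or exit |
| 4.1.1 | every event, compared across phases | all phases, so Phase IV too |
| 4.1.4 | every event | explantation |
| 4.1.4 | only events linked to device or therapy | after explantation |
| 4.1.5 | serious events | the 4.1.4 period |
| 3.3 | serious and non-serious effects | no window given |
| 4.2 | monitoring activities | end of participation |

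The conflict of 4.1.4 and 4.1.5 with 4.1 is direct. With 4.1.1 it follows from the scope of the endpoint and the phase comparison. Sections 3.3 and 4.2 point the same way but are soft support: the first sets no window, and the second does not say that every event is logged.

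**2. Does the relatedness scale close the gap?** The scale in 4.1.4 has five categories. Four (definitely, probably, possibly, unlikely) are defined by reference to stimulation. The fifth, unrelated, covers an event explained by the clinical state or by any other cause. None names implantation, explantation or TMS. A wound infection after removal, or a seizure provoked by Phase IV TMS, fits the unrelated category as written. So the rule that keeps related events after explantation need not retain them.

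**3. Time affected.** Section 3.2 gives 8 weeks of baseline, 1 to 2 weeks of surgery, 60 months of decoding and stimulation, and a follow-up described as about 8 weeks after explantation. I assume that the last is a duration; it could also be read as a time point.

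- 60 months = 5 × 365.25 / 7 = 260.9 weeks
- Total = 8 + 1 + 260.9 + 8 = 277.9 weeks, or 278.9 with 2 weeks of surgery
- Share outside the all-event log = 8 / 278 = 2.9%
- Largest total = 8 × 5 = 40 participant-weeks
- TMS rounds outside the log = 1 (Phase IV) of 2 (Phases I and IV)

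**4. The seizure control against the criterion.** The hazard text names two exclusions. The pacemaker half is in 3.1.1, under other implanted devices. The seizure half is not matched. Someone with one remote seizure, or with a seizure disorder no longer under care, has a seizure history but does not meet the listed criterion. Entry screening also cannot detect a first seizure during the study.

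**The case against.** **The gap is narrow.** Reporting does not stop at explantation, because device- or therapy-related events are still reported. Sections 3.3 and 4.1.1 ask separately for surgery-related effects. What is lost is chiefly events judged unrelated, over a few weeks, in a feasibility study that 4.5 says will not support an approval. This stands as a limit on size. It does not remove the conflict, because what counts as unrelated depends on a scale that leaves out surgery and TMS. One could stretch the word stimulation to cover TMS, which 3.2.5 describes as a brain stimulation method, but that would still not cover the removal operation.

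**The VR control is already in the protocol.** The hazard text is itself protocol text, 4.5.1 does not say that controls must sit in 3.1.1, and the co-morbidity list is illustrative, so an investigator could exclude a past seizure by judgement. The headset is optional, and the quoted VR seizure risk is 1 in 4,000, or about 0.12% for 5 people (1 − (1 − 1/4000)^5). All of this is fair. It makes the mismatch small, but a stated exclusion and a discretion are different things, and screening staff work from the criteria.

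**Stronger readings that the documents do not support.**

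- A reader might turn the 2% for TMS into a seizure probability for Phase IV. It has no denominator or time unit and comes mostly from people with known seizures. The relevant quantity, the chance of an on-study seizure times the TMS risk given one, cannot be obtained from the documents.
- A reader might take the lack of a stated seizure check before Phase IV TMS as proof that none exists. That is an argument from silence. The case report forms are an appendix outside the supplied text, seizures up to explantation are on the log, and 4.1.1 lets investigators end participation for onset of epilepsy.
- A reader might infer that reporting of unanticipated device effects is seriously weakened. Seizure is already an identified risk in several sections, so an ordinary seizure would rarely qualify under 4.1.3 in any case.
- A reader might want a numerical bias for the phase comparison. The share of post-explant events that would be judged related is unknown, so none can be given.

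**Conclusion.** The concern holds in two parts, the first more important than the second.

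First, 4.1.4 and 4.1.5 contradict 4.1 and cannot deliver the safety endpoint in 4.1.1 after explantation. The stretch affected is about 8 weeks per participant, 2.9% of the planned time and at most 40 participant-weeks, if the follow-up entry in 3.2 is a duration. It is short, but it contains recovery from a second intracranial operation and one of the two TMS rounds. If staff follow 4.1 in practice nothing is lost; the text does not say which section governs.

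Second, the seizure exclusion credited as a VR control is broader than the listed criterion. The practical risk is small on the protocol's own VR figure, and the correction is simple.

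Neither part shows that a participant has been or will be harmed, or that the primary outcome is affected. A seizure check before the repeat TMS is a sensible minor addition rather than a demonstrated defect. Both main corrections should go into the next amendment.

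**What to change.** 1. In 4.1.4 and 4.1.5, extend the log of every event, and serious-event reporting, to study exit, so that they agree with 4.1 and 4.1.1.
2. Add to the relatedness scale a judgement on study procedures: implantation, explantation and TMS.
3. Make 3.1.1 and the VR hazard text in 4.5.1 say the same thing: anyone with a prior or on-study seizure does not use the VR headset and works with the screen display that 3.2.3 already allows. There should be no investigator override, since that would weaken a control now stated without conditions. A rule on headset use need not reduce enrolment.
4. As a minor addition to 3.2.4, confirm before Phase IV TMS whether there has been any seizure since baseline, including during explant recovery, and record the reason if TMS is omitted.

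**Cost.** One amendment, a short question at a visit already planned, and about 8 more weeks of event logging for each of up to 5 participants. A participant with a seizure may have no post-explant TMS map. The planned fMRI would still show a shift in movement representations, but the corticospinal plasticity measure in 3.2.5 would be missing for that person.
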